**PROSPECTIVE, MULTICENTRIC, BEFORE AFTER STUDY TO  
EVALUATE THE EFFECTIVENESS AND THE SAFETY OF A MEDICAL  
DEVICE IN THE TREATMENT OF COMMON WARTS AND PLANTAR  
WARTS**

Clinical investigation plan #:	23E2007
NCT number:	NCT06214559
Date and version :	V1.0 of 27.10.2023
Title of the clinical investigation:	PROSPECTIVE MULTICENTRIC, BEFORE AFTER STUDY TO EVALUATE THE EFFECTIVENESS AND THE SAFETY OF A MEDICAL DEVICE IN THE TREATMENT OF COMMON WARTS AND PLANTAR WARTS
Sponsor:	PODERM Professional Swiss Footcare Laboratories [name] SWITZERLAND
Development phase:	Exploratory study Interventional MD without CE mark
Objectives:	
Primary objective: To evaluate the effectiveness of Sérum VERRUPRO® in the treatment of warts, assess by the evolution of the wart diameter after 35 days of treatment.
 
Secondary objectives:
 
 
- To evaluate the effectiveness of Sérum VERRUPRO® in the treatment of warts, assessed by the investigator , after 35 days of treatment.
 
- To evaluate the effectiveness of Sérum VERRUPRO® in the treatment of warts assess by the investigator clinical examination, after 35 days of treatment.
 
- To illustrate the effectiveness of Sérum VERRUPRO® on the skin aspect before and after the treatment assess by photographs.
 
- To evaluate the patient's opinion of Sérum VERRUPRO® on the effectiveness, tolerance, and acceptability after 35 days of treatment.
 
- To evaluate the safety and tolerance of Sérum VERRUPRO®
 

Design:	Prospective, multi center, before/after study.
Planned Sample Size:	33 included patients to expect result on 30 patients. 60% of patients will be treated for a wart on their back of hands or fingers. 40% of patients will be treated for a plantar wart.
Number of investigational study sites:	2 sites in Tunisia
Inclusion criteria:	
 
1. Patient having given freely her/his informed, written consent.
 
2. Patient having a good general health.
 

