Endpoints:	
Primary endpoint  Clinical examination performed by the investigator to evaluate the diameter of the wart at D0 and 35 days after treatment.  The effect of the product on clinical parameters will be evaluated by comparing the mean diameter before and after treatment.
 
Secondary endpoints:
 
 
- The global improvement of the wart will be assessed by the investigator after 35 days of treatment.
 
- Clinical examination performed by the investigator to evaluate the roughness, thickness and the number of dermal papillae of the wart at D0 and 35 days after treatment.  The effect of the product on these clinical parameters will be evaluated by a comparison before and after treatment.
 
- Illustration of the effectiveness of Sérum VERRUPRO® on the skin aspect before and after the treatment with photographs.
 

	
 
- Analysis of the answers to the patient questionnaire regarding effectiveness, tolerance, and acceptability of the investigational device 35 days after treatment.
 
- Products safety will be assessed by collection of Adverse Events (AEs) throughout the study. AEs will be summarized and tabulated by severity, causality, action taken and outcome, using descriptive statistics.
 
- Product tolerance will be assessed by the investigator at D0 (before the product use) and D35 by a clinical examination.
 

Study Procedures:	
Visit 1: informed consent, medical interview, collection of medical history and previous treatment, checking of the inclusion and exclusion criteria, patient inclusion, selection of the studied wart, clinical examination of the wart by the investigator, tolerance parameter evaluation, preparation of the wart by the investigator (removal of the stratum corneum if needed), photography of the selected wart, application of the product by the patient, distribution of daily log and product.
 
Visit 2: clinical examination by the investigator, tolerance parameter evaluation, photography of the selected wart, assessment of the global improvement by the investigator, patient subjective questionnaire, product tolerance evaluation, record of AE, concomitant treatments, study end.

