Statistical methods:	
The following analysis populations will be studied and will be considered for the statistical analysis:
 
 
- Safety population: any patient having used the investigational device.
 
- ITT (Intent-to-Treat): any patient included in the study with at least a post-basal value.
 
- PP population: any patient included having used at least once the investigational device and without any major deviation to the CIP.
 
 
Descriptive analysis: Quantitative data will be summarized using adapted statistics (number of values, number of missing values, mean, standard deviation, minimum and maximum values) by time point. Categorical data will be summarized in frequency (N) and percentage (%).
 
Primary endpoint: To evaluate the effectiveness of Sérum VERRUPRO® in the treatment of warts, assessed by the evolution of the wart diameter after 35 days of treatment. Clinical examination will evaluate the diameter of the wart at D0 and 35 days after treatment. The effect of the product on clinical parameters will be evaluated by comparing the mean before and after treatment.
 
A paired t-test will be carried out on the change from baseline outcome (D35-D0) to assess whether the mean value of the diameter of the wart decrease significantly from baseline.
 
Secondary endpoints:
 
 
- Global improvement Clinical examination of roughness, thickness and number of dermal papillae.
 
- Subjective evaluation by the patient.
 

	
 
- Tolerance by the investigator
 
 
Each secondary endpoints listed above, will be summarized using adapted statistics.
 
Safety assessment by collecting all the AEs occurred during the study will be summarized in frequency and percentage for the Safety population.
 
Each statistical analysis test will be two tailed with a type I error set at <math>\alpha=0.05</math>.
 
Statistical software : SAS v9.4

Foreseen study duration:	
Clinical investigation beginning: Q4 2023
 
Clinical investigation end: Q2 2024
 
Clinical investigation global duration: 4 months
 
Duration by patient: 35 days

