#### FLOW-CHART

Procedure	Visit 1 Day 0	Visit 2 Day 35
Days	D0	D35±7
Informed consent form signature	●	
Medical interview, medical history, previous and concomitant medications collection by the investigator	●	
Checking of the inclusion and exclusion criteria	●	
Patient inclusion	●	
Selection of the studied wart	●	
Clinical examination (diameter, roughness, thickness, dermal papillae) by the investigator	●*	●
Preparation of the selected wart (removal of the stratum corneum if needed) by the investigator	●	
Clinical examination for evaluation of product tolerance by the investigator	●*	●
Photograph of the selected wart	●* (after removal of the stratum corneum)	●
Treatment application by the patient	● (under investigator control at the site on D0 then at home)	
Patient subjective evaluation questionnaire		●
Global improvement evaluation by the investigator		●
Distribution of daily log and products	●	
AE and concomitant treatment collection	●	●
Study end		●

\*Before treatment application

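### AE percentages count every device user, but Visit 2 is the only safety assessment scheduled after D0, so patients who miss it and report nothing can lower the AE rate unseen

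*Combined protocol and SAP*

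**What the plan says.** The Statistical methods section of the synopsis sets the denominator: "Safety population: any patient having used the investigational device". It then states the AE summary: "Safety assessment by collecting all the AEs occurred during the study will be summarized in frequency and percentage for the Safety population". The flow-chart places the first application at the site on D0, with the investigator supervising.

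On collection, the Endpoints section says "Products safety will be assessed by collection of Adverse Events (AEs) throughout the study" and "AEs will be summarized and tabulated by severity, causality, action taken and outcome, using descriptive statistics". The flow-chart row "AE and concomitant treatment collection" is marked at two visits only, D0 and D35±7. For tolerance, the Endpoints section says "Product tolerance will be assessed by the investigator at D0 (before the product use) and D35 by a clinical examination". The patient questionnaire, which also covers tolerance, is given only at D35.

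A daily log is handed out at Visit 1. Its content is not described, and neither Visit 2 under Study Procedures nor the flow-chart lists its return or review. No contact between the two visits and no assessment for patients who leave early is shown.

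The Planned Sample Size entry reads "33 included patients to expect result on 30 patients". Under Descriptive analysis, a count of missing values is promised for quantitative data. Categorical data get only a frequency and a percentage.

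**The concern.** The numerator and the denominator of the AE percentage rest on different follow-up. A patient enters the denominator at the first application. Apart from a reaction seen at the site on D0, the same patient can enter the numerator only by attending Visit 2 or by reporting an event unprompted. The scheduled post-treatment AE record, tolerance examination and questionnaire all depend on that one visit.

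Local intolerance is a plausible reason to stop a topical product, so patients who disappear before D35 may differ from those who return. If they do, the AE percentage is too low and the D35 tolerance summary describes only those who came back. There is no control arm in which the same under-capture would occur and could be compared.

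Safety and tolerance are stated objectives for a device that has no CE mark, and with 33 patients a few uncaptured events change the picture. An analyst cannot recover afterwards safety data that were never collected.

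**Working it through.** **Inputs**
- Patients included: 33; patients with results: 30 (Planned Sample Size).
- AE denominator: all users (Statistical methods). This is taken as 33, because first use is at the site on D0 (flow-chart).
- Scheduled safety assessments after D0: one, at D35±7 (Study Procedures, flow-chart).
- Number with no safety data after D0, m: not given. m = 3 is an assumption taken from the sample-size allowance; m = 1, 2 and 5 show the range.
- AE counts x among assessed patients: illustrative, since the documents give no expected AE rate.

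**Step 1: the plan's own figure.** The implied loss is (33 − 30)/33 = 3/33 = 9.1%. No dropout rate is stated. An assumed 9% gives 30/(1 − 0.09) = 33.0, so 33. An assumed 10% gives 30/(1 − 0.10) = 33.3, so 34, or 30 × 1.10 = 33 by simple inflation. The 33 is therefore consistent with an allowance of about 9 to 10%. The 30 cannot be derived, because no effect size, SD or power is given.

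**Step 2: reported rate and possible rate.** With x patients with an AE among those assessed and m patients with no post-D0 data:
- reported rate = x/33
- highest possible rate = (x + m)/33
- understatement = between 0 and m/33

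For m = 3, with exact (Clopper-Pearson) 95% intervals:

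| x | Reported, x/33 | Among the assessed, x/30 | Highest possible, (x + 3)/33 |
|---|---|---|---|
| 0 | 0.0% (0.0–10.6) | 0.0% (0.0–11.6) | 9.1% (1.9–24.3) |
| 3 | 9.1% (1.9–24.3) | 10.0% (2.1–26.5) | 18.2% (7.0–35.5) |
| 6 | 18.2% (7.0–35.5) | 20.0% (7.7–38.6) | 27.3% (13.3–45.5) |

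**Step 3: other numbers unassessed.** The largest understatement, m/33, is 3.0 points for m = 1, 6.1 for m = 2, 9.1 for m = 3 and 15.2 for m = 5.

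**Step 4: what drives it.** At x = 3, dividing by 30 instead of 33 moves the rate only from 9.1% to 10.0%. The choice of denominator matters little. What matters is whether the unassessed patients had events nobody recorded: at x = 3 the rate could double, to 18.2%. Changing the denominator would not cure this; collecting the data would.

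**Step 5: would the tables show it?** An AE table is categorical, so under the Descriptive analysis text it carries no count of patients without information. A patient who was asked and had no AE looks the same as a patient who was never asked. For tolerance, a patient who misses Visit 2 keeps the D0 value, taken before use, and has no post-treatment value.

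**The case against.** The strongest reply is that the plan does not limit AE capture to the visits. It says "Products safety will be assessed by collection of Adverse Events (AEs) throughout the study", and the analysis covers all AEs that occurred. A patient who stops in the first week for burning and reports it is in the numerator whether or not Visit 2 takes place, and the stop could appear under action taken. The daily log may hold further information. This stands, and it limits the point to patients who stop, miss Visit 2 and report nothing. It does not remove the point: the statement gives an intention, while the procedures shown provide no contact that would carry it out for someone who does not return, and no step recovers the log.

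A reader might infer that everyone who stops early is counted as AE-free and drops out of the tolerance table. The documents do not support that. Nothing shown ends participation when the product is stopped, a patient who stops but attends D35±7 is fully assessed, and no sentence says that lost patients are free of AEs.

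A reader might also infer that the plan expects 3 patients without safety data. The allowance of 3 has no stated reason, and some of these patients could attend Visit 2 and be set aside for protocol deviations.

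Defining the Safety population as all users is conventional and is not itself a fault. The available text is a synopsis and a flow-chart, so a withdrawal procedure may be described elsewhere; if so, the flow-chart should show it. Finally, this is a descriptive summary in an exploratory study, which limits how much weight the figure will carry.

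**Conclusion.** The point holds in a limited form. As shown, the plan has no safety contact for patients who miss Visit 2 and no rule for how they enter the AE and tolerance summaries. Those who also report nothing are implicitly counted as having no AE. The AE percentage can therefore be biased downward, and the tables would not reveal it.

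With 3 such patients the understatement lies between 0 and 9.1 percentage points. The upper end is a worst case: all 3 must lack data after D0, all must have had an AE, and none may have been captured by report or log. If none of them had an AE, there is no bias. It would therefore be wrong to say that the AE rate is biased by 9.1 points, or that it is certainly biased at all. The primary diameter analysis is not affected by this point. The change is worth making because it is cheap, serves a stated objective, and cannot be made once the patients have gone.

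**What to change.** **In the flow-chart and Study Procedures**
- Add a safety contact for any patient who stops early or misses Visit 2. If the patient attends, use the existing AE record and tolerance examination. Otherwise make a telephone AE enquiry that covers the date of and reason for stopping.
- State that this contact is additional to the D35 visit and does not replace it for patients who still attend, so that their D35 data are kept.
- List return and review of the daily log, and say how its entries feed the AE record.

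**In the AE and tolerance tables**
- Beside each percentage, give the number of Safety-population patients with safety data after D0.
- List discontinuations with their reasons. The text shows no tolerance scale, so a listing is safer than scoring early stopping as a new, undefined tolerance category.

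**Cost.** On the plan's own allowance this is about 3 calls or visits by the same investigator using existing assessments, and one extra table line. The reported AE rate may look slightly less favourable. The Safety population definition and the primary analysis stay as they are.

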#### FLOW-CHART

Procedure	Visit 1 Day 0	Visit 2 Day 35
Days	D0	D35±7
Informed consent form signature	●	
Medical interview, medical history, previous and concomitant medications collection by the investigator	●	
Checking of the inclusion and exclusion criteria	●	
Patient inclusion	●	
Selection of the studied wart	●	
Clinical examination (diameter, roughness, thickness, dermal papillae) by the investigator	●*	●
Preparation of the selected wart (removal of the stratum corneum if needed) by the investigator	●	
Clinical examination for evaluation of product tolerance by the investigator	●*	●
Photograph of the selected wart	●* (after removal of the stratum corneum)	●
Treatment application by the patient	● (under investigator control at the site on D0 then at home)	
Patient subjective evaluation questionnaire		●
Global improvement evaluation by the investigator		●
Distribution of daily log and products	●	
AE and concomitant treatment collection	●	●
Study end		●

\*Before treatment application
